6.2. Enrolment and Screening

Women with benign gynaecological conditions requiring a hysterectomy and who are suitable for either surgical technique are eligible for inclusion in the LAVA trial.

Prior to clinical consultations, the medical records of potential participants may be screened for eligibility by clinic doctors, nurses, research nurses and research

midwives, after having received appropriate training relating to the trial. Clinic doctors will confirm eligibility for the trial.

6.3. Randomisation

Randomisation will be provided by a secure online randomisation system at the Birmingham Clinical Trials Unit (BCTU) (available at <http://www.trials.bham.ac.uk/lava>). Unique log-in usernames and passwords will be provided to those who wish to use the online system and who have been delegated the role of randomising participants into the study as detailed on the LAVA Trial Signature and Delegation Log. The online randomisation system will be available 24 hours a day, 7 days a week, apart from short periods of scheduled maintenance. A freephone telephone randomisation service ([name]) is available Monday to Friday, 09:00 to 17:00 UK time, except for bank holidays and University of Birmingham closed days.

After participant eligibility has been confirmed and informed consent has been received, the participant can be randomised into the trial. Randomisation Notepads will be provided to investigators and may be used to collate the necessary information prior to randomisation. All questions and data items on the Randomisation Notepad must be answered before a Trial Number and allocation can be given. If data items are missing, randomisation will be suspended, but can be resumed once the information is available. Only when all eligibility criteria and baseline data items have been provided will a Trial Number be allocated.

Participants will be randomised at the level of the individual in a 1:1 ratio to undergo their hysterectomy by either a laparoscopic or open abdominal route.

A minimisation algorithm will be used within the online randomisation system to ensure balance in the treatment allocation over the following variables:

- Previous caesarean section (yes / no)
- BMI (≤ 29.9 , 30-34.9, ≥ 35 Kg/m²)
- Uterine Size (≤ 12 weeks, > 12 weeks)
- Planned retention of cervix (yes / no)
- Recruiting centre

A 'random element' will be included in the minimisation algorithm, so that each patient has a probability (unspecified here), of being randomised to the opposite treatment that they would have otherwise received. Full details of the randomisation specification will be stored in a confidential document at BCTU.

Following randomisation, a confirmatory e-mail will be sent to the randomiser, the local PI and the trial co-ordinator, with the participant's unique trial number.

Investigators will keep their own study file log which links patients with their allocated trial number in the LAVA Patient Recruitment and Identification Log. The Investigator must maintain this document, which is not for submission to the Trials Office. The Investigator will also keep and maintain the LAVA Screening Log which will be kept in the ISF and which should be available to be sent to the Trials Office upon request. The LAVA Patient Recruitment and Identification Log and LAVA Participant Screening/Enrolment Log should be held in strict confidence.

6.4. Informing the participant's GP

If the participant has agreed, the participant's GP will be notified that they are in LAVA trial by using the LAVA GP Letter. If the woman does not want her GP to be aware of her participation in the LAVA study then she may opt out of this on the consent form.

6.5. Blinding

Due to the differing natures of the intervention it is impossible to blind either the care providers, investigators or participants to their allocated group.

7. TRIAL TREATMENT / INTERVENTION

7.1. Trial Treatment

Hysterectomy undertaken by either a laparoscopic or an open abdominal route, by a surgeon who has self-declared as having expertise in laparoscopic hysterectomy, abdominal hysterectomy or both approaches to hysterectomy. However, to participate in the LAVA trial, these gynaecological surgeons will have to meet minimum standards, regarding experience and case-load, to be considered competent in a particular type of hysterectomy. Satisfactory experience will require surgeons to have performed a minimum of 30 cases and to have a current caseload of at least 12 cases per year. For surgeons to conduct both procedures, these criteria will need to be met for both procedures. In light of the unprecedented restrictions on elective operating for benign conditions imposed by the Covid 19 pandemic, the required surgical caseload can be determined from the year preceding the SARS-COV-2 viral outbreak in March 2020.

The decision to remove or retain cervix (total or sub-total) or remove and retain ovaries will be left to the discretion of the participant in consultation with her gynaecologist.

The expertise design process for eligible centres is depicted in the figure on the next page:

Expertise-based surgery process

Confirm eligibility of participating centre

Members of the Local Surgical Unit (LSU)¹ should:

- (1) Be able to provide laparoscopic AND open hysterectomy for benign conditions by surgeons who meet the threshold for expertise²
- (2) Have at least one surgeon willing to randomise to LAVA
- (3) Be able to agree local eligibility criteria (i.e. criteria to undertake either laparoscopic OR open hysterectomy)

Identify and confirm surgical expertise² within the participating centre

- Expert surgeon LAPAROSCOPIC
- Expert surgeon OPEN

Randomisation by local research team

Eligibility confirmed by a surgeon willing to randomise to LAVA³

Laparoscopic hysterectomy

Allocated LAPAROSCOPIC expert surgeon⁴

Open hysterectomy

Allocated OPEN expert surgeon⁴

1 Collective group of surgeons within a centre willing to operate on patients recruited into the LAVA trial. Not all surgeons within the LSU need to be willing to randomise but they should be prepared to perform a hysterectomy, according to their expertise, on patients following randomisation.

2 Surgeons to have performed a minimum of 30 cases and to have a current caseload of at least 12 cases per year. For surgeons to conduct both procedures, these criteria will need to be met for both types of hysterectomy. In light of the unprecedented restrictions on elective operating for benign conditions imposed by the Covid-19 pandemic, the required surgical caseload can be determined from the year preceding the SARS-COV-2 viral outbreak in March 2020.

3 The surgeon must consider the position for each individual patient. Only if they believe that either operation will be suitable for an individual patient can the patient then be recruited.

4 Participants must be made aware that their surgery may be conducted by another surgeon within the LSU with the appropriate expertise.

7.2. Accountability Procedures

The allocated intervention and the actual procedure that is undertaken will be recorded on a case report form (CRF). This completed CRF will be returned to the trials office where compliance will be monitored. Should any concerns arise then investigations will be undertaken to determine the reasons for changing the hysterectomy route or treatment and the findings presented to the TMG for their guidance. A summary of the compliance will be presented to the study oversight groups.

7.3. Treatment Modification

Modification of the hysterectomy pathway or treatment is undesirable but is allowed if there are legitimate medical reasons for this, or at the participant's request. The reasons why the hysterectomy pathway or treatment has changed will be recorded on a CRF that will be returned to the trial office.

Should any concerns arise then investigations will be undertaken to determine the reasons for changing the hysterectomy route, deviation from the planned surgery regarding removal of the ovaries and / or cervix or undertaking concomitant surgical procedures, or change to alternative surgical or medical treatment. The findings will be presented to the TMG for their guidance. A summary of the compliance will be presented to the study oversight groups.

The request to change treatment route, or the withdrawal of participants before the randomised treatment allocation has been performed should be an exception as women should be counselled as to the nature of the procedures before consenting to participate in the LAVA trial.

8. OUTCOME MEASURES AND STUDY PROCEDURES

Women who give consent in a face to face setting will subsequently complete their baseline questionnaires and then proceed to randomisation. Participants who consent remotely be sent the baseline questionnaires as paper copies to return in the post in self – addressed envelopes or in person if attending hospital for scheduled clinical visit. Alternatively, the baseline questionnaires will be made accessible via a secure weblink sent by email or SMS. These questionnaires can be completed and on-line.

The baseline questionnaires are self-explanatory but help to complete them will be provided by the local or central medical research teams on request using remote means (telephone / VOIP /video consultation) where feasible. Participants will be made aware of this resource by the local research teams. It is anticipated that some participants may need help to select their 8 personalised recovery targets from 29 options PROMIS-PF (Patient-Reported Outcomes Measurement Information System Physical Function) item bank v1.2^{16, 21-23}. Local research teams will offer remote (telephone, VOIP or video) contact, or exceptionally face to face appointments, to provide explanation.

Women will also have the opportunity to discuss all aspects of the proposed research with the local clinical team (staff at pre-admission clinics and ward staff while admitted), the Research Nurse, family and friends and, if appropriate, with their GP before admission.

8.1. Trial outcomes

8.1.1. Internal pilot outcome

We aim to recruit a minimum of 257 participants within 9 months of the first recruiting hospital being activated.

This is calculated on the assumption that 22 recruiting centres will be opened within this 9 month time-frame with a staggered starts and individual recruitment targets. If recruitment is =100% of expected (green), we will proceed to the main trial; if 67% to 99% of expected (amber), we will explore and implement methods to improve recruitment; if <67% of expected (red), and there are no obvious remedial factors, we will discuss with the TSC and consider stopping the trial. Any decision regarding the feasibility of the RCT, and remedial measures if necessary, will also be informed by the results for the embedded qualitative process

8.1.2. Primary Outcome

Major surgical complications. These will be objectively ascribed and largely in accordance with the validated and widely used Clavien-Dindo classification of surgical complications²⁴. They will be defined as any of the following up to and including six full weeks post-surgery: i) all Clavien-Dindo grade III-V complications ii) Clavien-Dindo grade II complications of pulmonary embolus or blood transfusion or; iii) haemorrhage \geq 1L or; iv) major adverse anaesthetic event (see table below).

The most commonly anticipated major surgical complications are:

- Haemorrhage \geq 1 L
- Blood transfusion
- Bladder injury
- Ureteric injury
- Bowel injury
- Vascular injury
- Unplanned removal of any other organ
- Any other complication not covered requiring surgical, endoscopic or radiological intervention
- Pelvic haematoma requiring radiological or surgical intervention
- Pelvic abscess requiring radiological or surgical intervention
- Life-threatening complication requiring admission to HDU/ITU

However, other less common major surgical or anaesthetic complications may arise and these will be ascribed in accordance with the appropriate Clavien-Dindo classification.

Definition of major surgical complications in the LAVA trial

Major haemorrhage	Haemorrhage \geq 1L
Clavien-Dindo grade II	Pulmonary embolus, blood transfusion
Clavien-Dindo grade III	Complication requiring surgical, endoscopic or radiological intervention
Clavien-Dindo grade IV	Life-threatening complication requiring management on a High Dependency Unit (HDU) / intensive therapy unit (ITU)*
Clavien-Dindo grade V	Death
Major anaesthetic event	Anaphylaxis, awareness, nerve injury (including epidural/spinal anaesthesia), hypoxic brain injury, malignant hyperthermia, iatrogenic complication (e.g. pneumothorax from central line, limb ischaemia from arterial line)

*Non-life threatening elective or precautionary admission to an HDU (e.g. because of medical co-morbidities) post-operatively will not be considered a grade IV complication.

Complication data occurring during and up to 6 weeks following hysterectomy will be collected from the relevant case report forms completed by the local research team:

- Day of Surgery CRF
 - Detailing the type of major peri-operative complications
- Post-operative inpatient CRF
 - Detailing the type and timing of major surgical complications occurring during inpatient stay up until hospital discharge)
- 6 week post-surgery complication and representation CRF
 - Detailing the type and timing of major post-operative complications, as well as any reattendance and / or readmissions to hospital up to 6 weeks post-surgery, will be recorded. The data will be acquired by the local research team from scrutiny of the hospital case-notes and / or follow up consultation (if conducted routinely at approximately 6 weeks post-hysterectomy). The "6 week follow up patient completed CRF" that reports overnight admission following hysterectomy will also be checked and corroborated by the TMG for consistency; see below.

The TMG will collate "6 week follow up patient completed CRFs" that report overnight admission following hysterectomy. If the corresponding "6 week post-surgery and representation CRF" does not record a major surgical complication then the local PI will be contacted by the TMG and asked to provide additional information to explain the apparent discrepancy (e.g. oversight by the local research team, invalid patient response, re-admission another hospital etc.), and the reason for the overnight hospital admission and any additional treatments. The local PI will be asked to record their response on a Data Clarification Form.

8.1.3. Secondary outcomes

8.1.3.1 Key secondary outcome

- Time from surgery to resumption of usual activities. To increase accuracy and to minimise recall bias, the validated, personalised PROMIS-PF (Patient-Reported Outcomes Measurement Information System Physical Function) item bank v1.2 will be used¹⁶. 29 items covering relevant activities for our study population will be used from the entire 121 item bank²¹. Every item contains five response categories.

At baseline participants will be asked to select 8 activities from this list of 29 that, in their view, would most reflect their day-to-day activities. In this way participants will create their personalised physical function short form. Participants will record when each activity is resumed, with full recovery being achieved once all 8 personalised activities have been resumed. Until all personalised activities have resumed participants will be asked to complete this weekly for the first 12 weeks, then fortnightly from week 13 to week 26 after which requests will cease.

8.1.3.2 Other secondary outcomes

- Surgical outcomes:
 - Duration of operation, (minutes)
 - Estimated blood loss, (ml)
- In hospital stay:
 - In hospital post-operative pain using a Numerical rating scale (NRS) (with 0 indicating no pain to 10 indicating maximum pain)*, measured daily
 - Total analgesia use*
 - Overall quality of recovery score taken from the Quality of Recovery 15 (QoR-15) questionnaire²⁵ (with 0 indicating worst recovery and 10 indicating best recovery), measured at approximately 24 hours post-operation*
 - Time from operation to discharge in days (the day of operation will be assumed to be day 1. i.e. discharge on day 2 = 2 days). Each part of a day will count as a whole day, e.g. discharge after 2.5 days = 3 days)
- Up to 14 days after surgery:
 - post-operative pain using a Numerical rating scale (NRS) (with 0 indicating no pain to 10 indicating maximum pain), measured daily
 - Total analgesia use

- Up to 6 weeks post-surgery:
 - Minor complications (Haemorrhage 500mL to ≤ 1 L; pyrexia [presumed infection] requiring antibiotics; pain uncontrolled with usual analgesic management; urinary retention requiring re-catheterization; catheterisation for longer than 72 hrs; pelvic haematoma NOT requiring radiological or surgical intervention; pelvic abscess NOT requiring radiological or surgical intervention; wound infections/complications managed at the bedside or on the ward)
 - Representation to hospital
 - Readmission to hospital
 - Use of health services
 - Time away from normal activities

- 6 weeks post-surgery:
 - Quality of life score using EuroQol-5D-5L questionnaire²⁶ (with -0.285 indicating worst possible value and 1.0 as best possible value)
 - Quality of life score using EuroQol-5D-5L visual analogue scale (with 0 indicating worst possible score and 100 as best possible score)

- 12 weeks post-surgery:
 - Quality of life score using EuroQol-5D-5L questionnaire²⁶ (with -0.285 indicating worst possible value and 1.0 as best possible value)
 - Quality of life score using EuroQol-5D-5L visual analogue scale (with 0 indicating worst possible score and 100 as best possible score)
 - Time from surgery to work (if working) in days
 - Work productivity and activity impairment scores using WPAI-GH questionnaire²⁷ (absenteeism score; presenteeism score; work productivity loss score; activity impairment score – all scored 0 good to 100 bad) at 12 weeks only

- 12/24/36 months post-surgery:**
 - Satisfaction with hysterectomy (5-point Likert scale ranging from very satisfied to very unsatisfied)
 - Symptoms of urogenital prolapse using the Pelvic Organ Prolapse Symptom Score (POP-SS) questionnaire²⁸ (score ranging from 0 no symptoms to 28 maximum symptoms)
 - Bladder function using Urogenital Distress Inventory (UDI)^{29, 30} questionnaire (score ranging from 0 good to 100 bad)
 - Bowel function using Defecatory Distress Inventory (DDI)³¹ questionnaire (overall score ranging from 0 good to 100 bad)
 - Sexual function using the Sexual Activity (SAQ) questionnaire³² (pleasure score ranging from 0 worst to 18 best; discomfort score

ranging from 0 worst to 6 best; habit score ranging from 0 worst to 3 best)

- Quality of life score using EuroQol-5D-5L questionnaire (as scored above)
 - Quality of life score using EuroQol-5D-5L visual analogue scale (as scored above)
 - Body image using the Body Image Scale (BIS) questionnaire³³ (score ranging from 0 no disturbance to 30 maximum disturbance)
 - New gynaecological symptoms (abdominal pain [cyclical, non-cyclical and dyspareunia] and vaginal bleeding; yes/no)
 - Contact with Community Social and Clinical Care Services i.e. outpatients or emergency visits, and hospital services e.g. re-presentations, re-admissions, outpatient appointments and further medical treatment, time away from normal activities (collect to inform that Health Economic assessment [section 15]; not reported separately)
- Throughout: Serious adverse events (see section 9)

* Questionnaire may be completed at home if patient discharged on the same day as surgery

**The latter two time-points will only be collected for participants who reach these times prior to the study closes after all patients have been followed up for 12 months.

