9.2. Adverse Events (AE) non-CTIMPs

All medical occurrences which meet the definition of an AE should be reported. Please note this includes abnormal laboratory findings.

Peri-operative and post-operative complications experienced by the participants are the primary outcomes of the LAVA study. Complications arising from the interventions will be collected on the relevant CRFs.

As these events are well characterised, it is highly unlikely that this trial will reveal any new safety information relating to this intervention. The recording of selected AEs will therefore not affect the safety of participants or the aims of the trial. As such the following will not be classed as adverse events and so do not need to be reported as AEs:

- Haemorrhage \geq 1L
- Surgical Complications (any factor that comprises the Clavien-Dindo grade [II-IV] with or without hospitalisation or prolongation of existing hospitalisation)
- Anaesthetic complications
- Additional Medication required above that normally expected
- Emergency presentations / admissions
- Routine re-presentations / admissions for pre-planned events
- Prolonged hospitalisation without an associated adverse event
- Vaginal bleeding
- Pelvic organ prolapse
- Abdominal pain [cyclical / non-cyclical, and dyspareunia]
- Conditions / symptoms arising from altered bowel or bladder function

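### A haemorrhage of exactly 1 L falls in both the major (primary) and the minor (secondary) complication class, because the two definitions share that boundary

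*Protocol*

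**What the plan says.** Section 8.1.2 (Primary Outcome) defines the composite of major surgical complications. One component is "iii) haemorrhage \geq 1L or; iv) major adverse anaesthetic event". The same threshold appears in that section's list of anticipated complications and in its definition table. Section 9.2 uses it again when naming events that need no separate adverse event report: "Haemorrhage \geq 1L". The window for the composite is "any of the following up to and including six full weeks post-surgery".

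Section 8.1.3.2 (Other secondary outcomes) has a block headed "Up to 6 weeks post-surgery". Its first item opens with "Minor complications (Haemorrhage 500mL to" and then gives the upper limit; with that limit and the next entry it reads "Minor complications (Haemorrhage 500mL to ≤ 1 L; pyrexia [presumed infection] requiring antibiotics".

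Section 13.2 treats secondary outcomes other than the key one as exploratory, with no multiplicity adjustment.

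**The concern.** Two severity classes of one event, measured over one time window, would normally be exclusive. Here both include their common boundary. Followed literally, a woman with a 1 L bleed is counted once in the primary outcome and once among the minor complications, and the minor-complication rate includes events that the protocol elsewhere calls major.

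The rest of the minor list suggests that this was not intended. Pelvic haematoma and pelvic abscess are minor when no radiological or surgical intervention is needed, and major in section 8.1.2 when it is. Those pairs are exact complements; haemorrhage is the pair that overlaps.

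What is at stake is a clean definition of one exploratory outcome, and avoiding two instructions for the same event.

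**Working it through.** **Inputs**

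- Major haemorrhage: volume ≥ 1 L (8.1.2 text, list and table; same threshold in 9.2).
- Minor haemorrhage: 500 mL ≤ volume ≤ 1 L (8.1.3.2).
- Window: six weeks after surgery for both.
- Precedence or exclusivity rule: none found in the protocol. The statistical analysis plan was not available.

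**Step 1: is the sample size involved?** Section 13.1 uses a 6% rate in both arms, a 3% margin, a one-sided 2.5% level and 90% power.

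- Per arm: n = (1.960 + 1.282)² × 2 × 0.06 × 0.94 / 0.03² = 10.507 × 0.1128 / 0.0009 ≈ 1317, so 2634 in total, as stated.
- Clustering: 1 + (9 − 1) × 0.02 = 1.16, and 2634 × 1.16 = 3055, as stated.
- Loss to follow-up: 3055 / (1 − 0.06) = 3250, as stated.

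These figures depend on the primary definition only. A change to the minor category leaves them as they are.

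**Step 2: classify volumes around the limits**

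| Volume (mL) | Major as written | Minor as written | Minor if upper limit is < 1 L |
|---|---|---|---|
| 499 | no | no | no |
| 500 | no | yes | yes |
| 999 | no | yes | yes |
| 1000 | **yes** | **yes** | no |
| 1001 | yes | no | no |

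The overlap is the single value 1000 mL. With a strict upper limit the classes are exclusive and leave no gap between them.

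**Step 3: is the symbol a reading error from the PDF?** Probably not. Elsewhere the protocol text separates strict from non-strict inequalities, for example uterine size ≤ 12 weeks against > 12 weeks in section 6.3.

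**Step 4: effect on each outcome**

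- *Primary.* A 1 L bleed counts under 8.1.2 whatever 8.1.3.2 says, and a composite of any qualifying event counts a woman once. Change: zero.
- *Minor complications.* If analysed as yes or no per woman, let q be the share in an arm whose only minor item is a bleed of exactly 1 L. The arm's minor rate is then too high by q, and the risk difference shifts by q(laparoscopic) − q(abdominal). The protocol gives no figure for q in either arm, so no size can be attached.

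**The case against.** The strongest reply is that nothing of consequence is ambiguous. Section 8.1.2 states the 1 L threshold three times and section 9.2 repeats it, so a site that filed a 1 L bleed as minor only would be departing from the primary definition. The overlap touches one value. It puts a woman in two separately reported outcomes, and I found no place where the protocol adds major and minor complications together. A woman with another minor complication would add nothing extra to a per-woman count. All of this stands, and it limits the point to a correction of wording.

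A reader might infer more: that primary events will be lost because sites tick minor, and that the loss could be sizeable against the roughly 183 primary events expected (6% of 3055). The documents do not support this. It would need a CRF that carries the 8.1.3.2 wording, and the CRF is not shown. It would need sites to set aside 8.1.2, and the women concerned to have no other major component such as transfusion. It would also need a share of women at exactly 1 L, which the protocol does not give. Any percentage would be a guess, and women classified twice belong against the minor-complication count, not the primary count.

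Safeguards against misfiling exist but are partial. Estimated blood loss in mL is on the Day of surgery CRF (8.2.3), and trials staff check CRFs for consistency (11.4). The Trial Management Group's cross-check in 8.1.2 starts only from a patient-reported overnight admission, so it would not by itself pick up an operative bleed with no later admission.

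None of this makes the two definitions agree. Nor is it a detail left to the statistical analysis plan, since the protocol itself fixes both limits.

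**Conclusion.** The inconsistency is real and small. As written, a 1 L haemorrhage within six weeks is correctly a primary event and is also counted in the exploratory minor-complication outcome. The primary definition, sample size and non-inferiority test do not change. How many women are affected cannot be estimated from the protocol.

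The conclusion rests on the inequality symbols being as printed and on there being no precedence rule in a document not seen, such as the statistical analysis plan or the CRF completion guidance. If such a rule exists, the counting problem is already settled and only the protocol wording needs correcting.

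**What to change.** In section 8.1.3.2, change the minor haemorrhage category to 500 mL to < 1 L, and make any CRF wording match. Section 8.1.2 stays as it is.

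The operative blood loss recorded in mL may be used as a consistency check for intra-operative haemorrhage, by querying any case where the recorded class and volume disagree. It should not become the sole basis for classifying haemorrhage. It is a surgical outcome from the Day of surgery CRF, while both haemorrhage outcomes run to six weeks, and section 8.1.2 takes later complications from the inpatient and 6-week CRFs. Relying on the operative figure alone could miss post-operative haemorrhage.

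The cost is one symbol in the protocol and, if the CRF repeats the range, one there. No recalculation is needed.
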